8 DATA HANDLING AND RECORD KEEPING

We provide information on best practice in data handling and record keeping on our website

8. 1 Data Handling

8.1.1 DATASET CREATION

The study statistician will develop a standard schedule detailing the data points required and providing definitions. This will be discussed with the informatics team in each site to ensure comparable data can be provided. A data-sharing agreement will be established with each site. Data will be fully anonymised within the trusts prior to transfer, by the nominated member of staff in the trust responsible for extracting and compiling the data. Identifying information e.g. date of birth and postcode will be substituted with higher level information e.g. age and Super Output Area. Data will include local patient identifier numbers (a unique identifier for a patient within a health care provider); patients cannot be identified by these numbers once data are transferred

8.1.2 DATA TRANSFER

Trusts will Zip and encrypt data using 7-Zip software, and transfer using the University's secure Filedrop facility - https://filedrop.le.ac.uk/

8.1.3 Data Storage

All data will be stored on the University of Leicester r:drive and not transferred to personal devices. Access to the database will be restricted to study staff using a username and password. All data handling and record keeping will be kept in adherence to University of Leicester's and relevant NHS Organisation(s) policies.

8.1.3 DATA PROCESSING

Data will be processed at each of the three hospital sites, bringing together all required data into excel files. Once received by the University of Leicester the three excel files (one from each site) will be combined and analysed by the trial statistician.

8.1.4 DATA DESTRUCTION

Data will be destroyed 6 years after the end of study has been declared as per University of Leicester Policy. This will be undertaking by the study statistician, and observed by the University of Leicester *Deputy SIRO & Information Governance Lead (Research)*

8. 2 ACCESS TO DATA

Combined Protocol V3.0 22/07/24

Direct access will be granted to authorised representatives from the Sponsor, host institution and the regulatory authorities to permit project-related monitoring, audits and inspections.

8.3 ARCHIVING

Research data and archived files will be stored for a minimum of 6 years after the study has ended. Storage will comply with the University of Leicester archiving Standard Operating Procedure. Details can be found at: http://www2.le.ac.uk/offices/ias. Destruction of essential documents will require authorisation from the Sponsor.

9 MONITORING, AUDIT & INSPECTION

The study will be conducted in accordance with the current approved protocol, ICH GCP, relevant regulations and standard operating procedures.

The University of Leicester operate a risk-based audit programme to which this study will be subject to.

10 ETHICAL AND REGULATORY CONSIDERATIONS

10.1 RESEARCH ETHICS COMMITTEE (REC) REVIEW & REPORTS (ANNUAL AND FINAL)

The Lead Investigator and study statistician will ensure that participants' anonymity is maintained. No personal identifiable data will be available within the dataset. The Leicester team will make no attempts to identify participants within the dataset. If the statistician at Leicester notices that there is information in the database that can be used to identify any individual, general practitioner or general practice, they will inform the site immediately in writing, and the University of Leicester Information Assurance Team.

All delegated staff on the project with access to the data set will read and sign to say they will abide by the conditions of the data sharing agreement.

10.2 PEER REVIEW

This research has undergone extensive peer review during the course of the NIHR Health and Social Care Delivery Research funding process.

10.3 PUBLIC AND PATIENT INVOLVEMENT

Acceptability and Design

We convened a PPI group (Oct 2022) comprising six patients with experience of severe infection and hospital care to advise on study design (2F, 4M; 5 White British, 1 Asian). Group members were recruited from existing local PPI groups, and through informal contacts by the local Research Design Service PPI lead. The PPI engagement event took place online to enable participation from PPIE members who were unable to travel. The meeting consisted of a project presentation, where we presented our research questions and ideas for study design and methods.

Following the presentation, we invited an open discussion, allowing PPI group members to comment on all aspects of the presentation. PPI members were provided with a series of questions about study value and study design, and how we could involve patients in research, co-design, and dissemination. These were discussed during the meeting, and also sent to participants by email following the meeting inviting further feedback. In addition a further focused discussion was held online between [name] (PI) and [name] (PPI co-applicant). PPI feedback included the importance of considering patients from whom it is difficult to take blood, and for studying inequalities in blood sampling across patient groups, suggestions for patient involvement and the potential for patient-facing interventions, and dissemination suggestions. All feedback was taken into account in preparing this application. This includes:

- ensuring PPI representatives are involved in study team meetings
- providing training to all PPI members on research methods and on specific topics e.g. sepsis, antimicrobial resistance
- involving PPI members in analysis of qualitative data and in giving presentations of the findings
- producing Plain English summaries and a video about findings aimed at the public
- ensuring that patients are fully involved in the co-design process and consider the potential for a patient held/led intervention
- paying costs for PPI member conference attendance.

Undertaking, analysing and disseminating the research

- Research methods training and training on the clinical context will be provided to the PPI participants. Training will take place in year 1, and include online research methods training, and additional bespoke training in specific topics e.g. sepsis and antimicrobial resistance.
- PPI members will be involved in the analysis of findings, and in supporting dissemination. Members will also be asked to review and feedback on materials by email, with appropriate remuneration. Supporting dissemination will involve preparing Plain English summaries and social media materials, identifying dissemination routes, filming a video about the findings, participating in feedback presentations at participating hospitals, and attending national conferences (e.g., Health Services Research UK Conference).
- At the end of the project, we will run a half-day face-to-face PPI event. This will include a
 debrief, where PPI members are invited to reflect on their experience of participating in the
 project. We will further explore their interest in future study involvement (e.g. in follow-up
 research or separate projects). Finally, PPI members will be invited to attend the wider endof-project workshop alongside clinical and academic collaborators and other relevant
 stakeholders.
- In addition to the core PPI, we have a commitment from The Sepsis Trust and Antibiotic Research UK for support with some of our PPI activities, including helping us to engage with a wider group of patients with experience of infection to feed into latter stages of the codesign process, and to support public and patient dissemination of the outputs from our project.

10.4 PROTOCOL COMPLIANCE AND SERIOUS BREACHES

A study related deviation is a departure from the ethically approved study protocol or other study document or process or from Good Clinical Practice (GCP) or any applicable regulatory requirements. Planned deviations or waivers are not allowed however it is acknowledged that accidental protocol deviations may occur. Any deviations from the protocol will be

documented in a protocol deviation form and filed in the Trial Master File/Investigator Site File as applicable.

If a protocol deviation occurs, then the CI (or delegate) will document this in accordance with the University's Standard Operational Procedure (SOP) Identifying and Reporting Deviations and Serious Breaches of GCP and/or the Protocol.

Deviations from the protocol which are found to frequently recur will be explored and where necessary an amendment to the protocol will be made.

10.5 DATA PROTECTION AND DATA SUBJECT CONFIDENTIALITY

Data stored at the University of Leicester and analysed by the study statistician will be anonymised. All investigators will comply with the requirements of the Data Protection Act 2018 with regards to the collection, storage, processing and disclosure of personal information and will uphold the Act's core principles.

10.6 INDEMNITY

University of Leicester's insurance applies.

10.7 ACCESS TO THE FINAL PROJECT DATASET

Only, the Chief Investigator, researcher and co- investigators will have access to the full dataset. Direct access will be granted to authorised representatives from the Sponsor and host institutions for monitoring and/or audit of the study to ensure compliance with regulations

11 DISSEMINATION POLICY

Our approach to dissemination will aim for significant reach across diverse stakeholders. We will share knowledge about our findings, generate learning to drive improvements in practices along the preanalytic blood sampling pathway, provide initial evidence of feasibility and effectiveness of interventions to support applications for future research, inform ongoing NHSE work on optimising the blood culture pathway, and promote wider engagement and understanding of the research by patients and the public.

Dissemination will target: 1) Policy makers, national bodies including health professional organisations, and national interest groups; 2) Clinicians and healthcare professionals including microbiology staff and antimicrobials stewardship leads; 3) Academic audiences; 4) Patients and the public.

We will work closely with our patient and public contributors to develop and implement our dissemination plan, create appropriate outputs, and involve them in dissemination. The PPI co-applicant will lead on this. This will include the development of outputs, including creative outputs (infographics, short videos for hospital staff and the public) tailored to the needs and interests of patients and the public, and frontline healthcare staff. We will produce posters, videos that could be played in participating hospitals, and our PPI group members will attend presentations and external dissemination events to ensure that patient voice is heard.

We have strong links with the NHS England leads for improving the blood culture pathway across England, and will work with the NHSE Blood Cultures team to ensure we develop outputs that meet the needs of policy-makers. These connections will ensure the outputs have a direct pathway to impact for the national agenda. We will generate policy recommendations and disseminate through presentations at national AMR diagnostics policy board meetings and NHSE blood culture steering group. Through these connections we will reach influential national organisations including the UK Sepsis Trust and Antibiotic Research UK. We will also work through [name], the ED project lead, to engage with the

Emergency Medicine (the NIHR Emergency Medicine Incubator, the Royal College of Emergency Medicine and HEE Deanery leads for Emergency Medicine).

We have access to the international platform provided by The British Society for Antimicrobial Chemotherapy [BSAC] via [name] to support dissemination of, and engagement with our research findings, and we will disseminate our findings through the network of regional antimicrobial stewardship leads.

We will reach academic audiences by presenting findings at key national and international academic conferences, and we will contribute to the current evidence on optimising the blood sampling pathway through papers in high impact journals. This will include publications in both clinical and social science journals, allowing us to make an important contribution to the body of social science research in antimicrobial resistance. We will publicise key academic outputs through press releases, media interviews and through our research group Twitter feed. We will hold an end of project round table workshop for academics, and healthcare and policy stakeholders.

The study as a whole, including part 1a, will produce the following outputs:

- A bundle of interventions to optimise blood sampling practices for patients with suspected severe infection in acute care, which will be implemented across diverse health care settings; implementation guidance, and supporting materials including service blueprints.
- Presentations at participating hospital sites, 3 national conferences (e.g., BSAC annual conference, Health Services Research conferences (HSRUK), and the UK society for Behavioural Medicine Annual Scientific Meeting), and 1 international conference (e.g., European Congress of Clinical Microbiology & Infectious Diseases, European Health Psychology Symposium (EHPS)).
- Policy recommendations and presentations to regional and national leads, policy-makers and national healthcare and infection organisations at the National AMR Diagnostics board and the NHSE blood culture task and finish group.
- Four open access publications in high impact peer-reviewed journals
- Plain English summaries of research findings.
- Creative outputs to disseminate findings to patients and the public, and frontline hospital staff. This will include videos, mixed-media outputs and infographics, similar to outputs previously developed by members of the team: https://antimicrobialsinsociety.org/commentary/re-envisaging-infection-practice-ecologies-innursing-ripen/; https://vimeo.com/368059130?login=true)
- A dedicated project website
- Blogs and social media, including a publication in The Conversation, to publicise findings more widely.
- A final report to the HSDR programme board, which will synthesise the findings across the stages of the study, and will set out recommendations for future evaluation of the intervention bundle.

Publications and outputs will be available on open access via the University's Library database

Authorship eligibility guidelines and any intended use of professional writers

All members of the research team in its current form will be given authorship on the final study report and other outputs as appropriate.

Getting the bloods to the laboratory: developing interventions to improve the blood culture pathway for patient safety and antimicrobial stewardship (Part 1b).

SHORT STUDY TITLE / ACRONYM

Attitudes and Beliefs around blood culture sampling for treating acute infection

PROTOCOL VERSION NUMBER AND DATE: Protocol Version 1.0 – 25-06-2024

FUNDER: National Institute for Health and Care Research (NIHR156452)

Ethical Approvals: This protocol (part 1b) has received ethical approval from the University of Leicester Medical and Biological Sciences Research Ethics Committee (Ref 0457)

Short lay summary

Blood culture sampling is a diagnostic tool that is used to detect severe infection, like sepsis. Blood culture samples provide important clinical information that enables healthcare professionals to make decisions about patient treatment. This means that patients are more likely to get the right antibiotics for their infection, increasing their chances of survival and reducing antibiotic overuse and antimicrobial resistance. Previous research has shown that blood culture sampling does not always happen and if it does happen, samples are sometimes taken too late or not adhering to the required quality standards.

The purpose of this study is to find out why blood culture sampling is not always successfully undertaken. Specifically, we plan to conduct an online survey of UK healthcare professionals to measure their attitudes and beliefs towards blood culture sampling for acute hospital patients with suspected severe infection. We also want to find out what healthcare professionals identify as key barriers to successful blood culture sampling. To obtain representative results that generalise across hospital settings in England, we plan to recruit a national sample of healthcare professionals across different job roles and varying levels of seniority, who are involved in either requesting blood culture samples, taking blood culture samples or using the results from blood culture samples to inform their treatment. This will mean recruiting healthcare assistants, nurses and doctors, amongst other healthcare staff. We will recruit via two established cohorts of healthcare professionals, who previously gave consent to participate in research and provided their contact details for this particular purpose. Up to 400 participants will be recruited from the NHS CHECK and UK REACH cohorts and via social media and professional contacts and networks. Participants will complete an online questionnaire of approximately 20 minutes length. We will analyse the data to identify common attitudes around blood culture sampling and perceived barriers. We will also test whether attitudes differ across different professional roles or clinical settings. Finally, we will test what attitudes and beliefs may predict whether or not healthcare staff engage in blood culture sampling as part of their clinical activities.

This study is part of a wider project that aims to create a bundle of interventions to optimise blood culture sampling practices (IRAS 338495 and 332310).

Study Summary

Study Title	Attitudes and Beliefs around blood culture sampling for treating acute infection
Study Design	Quantitative: online survey
Study Participants	Healthcare professionals responsible for requesting blood culture samples, taking blood culture samples and/or using blood culture test results to inform clinical practice
Planned Size of Sample (if applicable)	400
Follow up duration (if applicable)	N/A
Planned Study Period	14 July 2024 – 30 May 2025
Research Question/Aim(s)	The primary research questions are:
	What are NHS healthcare professionals' attitudes towards blood culture sampling for adult patients with suspected severe infection? Do these attitudes differ by professional role and clinical setting?
	The secondary questions are:
	 Does our newly developed attitude questionnaire capture key components of the Theory of Planned Behaviour within the context of blood culture sampling? What are predictors of self-reported engagement in clinical activities that form part of the blood culture pathway? What are perceived barriers to healthcare staff engaging in clinical activities related to blood culture sampling for managing suspected severe infection? Do these perceived barriers differ by professional role or clinical setting?

1. Background

Blood culture sampling is a diagnostic tool that is used to detect severe infection in hospital patients. Blood sampled from patients is analysed in microbiology laboratories to detect the presence of bacteraemia (clinically significant bacteria in the bloodstream), to identify the type of bacteria causing the infection, and to measure the susceptibility of the bacteria to various antibiotics. This provides vital information to inform clinical decision-making about patient treatment (1), thereby increasing chances of patient survival (2, 3) and reducing antibiotic overuse and antimicrobial resistance.

In England in 2020, 55,000 patients were affected by antibiotic-resistance infections putting them at risk of poor outcomes and death, as well as contributing to increased healthcare costs (4). However, the use of antibiotics, particularly broad-spectrum antibiotics, continues to increase in hospitals in England (5). Despite the clinical importance of blood culture sampling, around half of hospital patients do not have blood samples taken at all when antibiotics are started, and when they are taken, they often fall shall of national quality standards (6-10). Optimising the blood culture pathway is a current priority for NHS England.

Blood culture sampling practices are underpinned by a range of behavioural, cultural and systems factors that may be difficult to address (11). Attitudinal barriers include the importance attached to blood culture diagnostics and views on the utility of blood culture sampling (12, 13). An unpublished systematic review of barriers and enablers to blood culture sampling identified a range of key barriers within the Theoretical Domains Framework domains of: knowledge, behavioural regulation, environmental connect and resources, memory, attention and decision processes, beliefs, and social influence (14). In our recent study involving interviews with acute care clinicians (15), we identified a range of barriers including lack of time and skills, problems of coordination and diffused responsibility, and lack of feedback on the consequences of blood cultures for subsequent patient management.

The purpose of this study is to find out why blood culture sampling is not always successfully undertaken and to increase generalisability of findings through taking a national sample of UK healthcare professionals. Specifically, we set out to assess the behaviours, beliefs and attitudes held by staff who prescribe antibiotics, take blood samples and/or use blood culture test results to inform clinical practice, about blood culture sampling and microbiological testing in acute care. We will also identify predictors of self-reported engagement in timely and appropriate blood culture sampling. This study is part of a wider project that aims to create a bundle of interventions to optimise blood culture sampling practices for acute care patients with suspected severe infection (IRAS 338495 and 332310).

2. Research Questions/Aim

The primary research questions for this study are:

- What are NHS healthcare professionals' attitudes towards blood culture sampling for adult patients with suspected severe infection?
- Do these attitudes differ by professional role and clinical setting? The secondary research questions are:
 - Does our newly developed attitude questionnaire capture key components of the Theory of Planned Behaviour within the context of blood culture sampling?
 - What are predictors of self-reported engagement in clinical activities that form part of the blood culture pathway?
 - What are perceived barriers to healthcare staff engaging in clinical activities related to blood culture sampling for managing suspected severe infection? Do these perceived barriers differ by professional role or clinical setting?

3. Study Design

This study will use a quantitative approach, using an online survey as a low cost and quick way of nationally sampling UK healthcare professionals across various clinical roles and grades increasing the generalisability of findings.

3.1. Study Participants

3.1.1. Sample size

The target sample size is 400 healthcare professionals. We considered sample size requirements across a number of different statistical analyses, which we are planning. For our plans to validate a new questionnaire measure, we followed White (2021)'s recommendation to sample 250-350 participants. For our ANOVAs, we ran a G*power calculation for ANOVA (repeated measures, between factors) with 4 groups and 4 measurements, assuming a correlation of up to 0.5. We estimated a power of .80 and an α error probability of .01 to detect a medium effect size f = .25, which returned 236 participants. For our linear multiple regression analysis (fixed model, R2 increase) with 10 predictors, we ran a G*power calculation, estimating a power of .80 and an α error probability of .01 to detect size f = .15, which returned 160 participants. To satisfy sampling requirements for all types of analyses and to account for potential data loss from incomplete submissions and exclusions, we will recruit up to 400 participants.

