We considered sample size requirements across our different analyses. Sample size recommendations for scale validation vary depending on the sample type used. For more specific samples (as opposed to samples drawn from the general population), 250-350 participants have been recommended (White, 2021). For our ANOVAs, we ran a G*power calculation for ANOVA (repeated measures, between factors) with 4 groups and 4 measurements, assuming a correlation of up to 0.5. We estimated a power of .80 and an α error probability of .01 to detect a medium effect size f = .25, which returned 236 participants. For our linear multiple regression analysis (fixed model, R² increase) with 10 predictors, we ran a G*power calculation, estimating a power of .80 and an α error probability of .01 to detect a medium effect size f = .15, which returned 160 participants. To satisfy sampling requirements for all types of analyses and to account for potential data loss from incomplete submissions and exclusions, we will recruit up to 400 participants.

8) Anything else you would like to pre-register?

(e.g., secondary analyses, variables collected for exploratory purposes, unusual analyses planned?) N/A

4. Agency UKHS. English surveillance programme for antimicrobial utilisation and resistance (ESPAUR) report 2020-2021. 2021.

5. Trust N. Antibiotic prescribing: Quality Watch 2024 [Available from:

https://www.nuffieldtrust.org.uk/resource/antibiotic-prescribing#background.

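### Part 1b sample size: the ANOVA figure of 236 does not follow from its stated inputs, which give 164, and the regression effect size labelled f = .15 should read f² = .15; the target of 400 is unaffected

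*Protocol*

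**What the plan says.** The Part 1b protocol (section 3.1.1) derives its target from three requirements: a scale-validation recommendation of 250 to 350, an ANOVA calculation and a regression calculation. Appendix 2 item 7 repeats all three.

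- **ANOVA.** The G*Power procedure is given as "ANOVA (repeated measures, between factors) with 4 groups and 4 measurements, assuming a correlation of up to 0.5". The result follows: "We estimated a power of .80 and an α error probability of .01 to detect a medium effect size f = .25, which returned 236".
- **Regression.** The procedure is a "linear multiple regression analysis (fixed model, R2 increase) with 10 predictors", and the result is reported as "estimating a power of .80 and an α error probability of .01 to detect size f = .15, which returned 160 participants". Appendix 2 item 7 adds an adjective: "to detect a medium effect size f = .15, which returned 160 participants".
- **Target.** To cover all analyses and allow for incomplete or excluded responses, "we will recruit up to 400 participants".

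**The concern.** Both calculations state their inputs fully enough to be rerun, apart from how the regression's predictors divide into tested and total. When they are rerun, the ANOVA inputs do not return 236, and the regression returns 160 only on a different effect-size scale from the one named.

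What is at stake is whether the statement of power is true. As written, a reader would conclude that 236 respondents give the ANOVA 80% power. The reader would also conclude that 160 respondents let the regressions detect f = .15, an effect explaining about 2% of variance. The same paragraph uses a genuine f (.25) for the ANOVA, and Appendix 2 calls both .25 and .15 medium, so two scales share one symbol. Appendix 2 is written in pre-registration form and its item 7 asks for precision about how the number is determined.

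**Working it through.** All powers come from the noncentral F distribution.

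**1. ANOVA, between-factor test with repeated measures**

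Inputs (section 3.1.1): k = 4 groups, m = 4 measurements, ρ = 0.5 (the upper end of the stated range), f = .25, α = .01, target power .80.

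Formula: λ = f² · N · m / (1 + (m − 1)ρ), with df = k − 1 and N − k.

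Substituting: λ = .0625 × N × 4 / (1 + 3 × 0.5) = 0.25N / 2.5 = 0.1N, with df = 3 and N − 4. N rises in steps of 4 to keep the groups equal.

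| N | λ | Power |
|---|---|---|
| 160 | 16.0 | .799 |
| **164** | 16.4 | **.812** |
| 232 | 23.2 | .9495 |
| **236** | 23.6 | **.954** |

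The smallest N reaching .80 is 164. The smallest N reaching .95 is 236.

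The words "assuming a correlation of up to 0.5" do not rescue 236, because a lower correlation reduces the requirement at power .80: 124 at ρ = 0.3 and 68 at ρ = 0. At power .80, 236 does appear at ρ = 0.9, where λ = 59 / 3.7 = 15.95 and power is .803, but that lies outside the stated range.

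**2. Regression, test of R² increase**

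Inputs (section 3.1.1): 10 predictors, α = .01, power .80, effect size .15 labelled f.

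Formula: λ = f² · N, with df = u and N − p − 1, where u is the number of predictors tested and p the number in the model.

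Reproducing the plan's figure: with f² = .15 and u = p = 10, N = 159 gives power .797 and N = 160 gives .801. So 160 is reproduced exactly.

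Taking the label literally: f = .15 means f² = .15² = .0225. The plan does not separate tested from total predictors, so a range is shown as an assumption:

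| Predictors tested, of 10 | N for power .80 if f² = .15 | N for power .80 if f = .15 | Power at 400 if f = .15 |
|---|---|---|---|
| 10 | 160 | 998 | .25 |
| 4 | 119 | 752 | .42 |
| 1 | 82 | 523 | .66 |

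The literal label exceeds 400 in every row, and no row under it gives 160.

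Variance explained: R² = f² / (1 + f²). For f² = .15 this is .15 / 1.15 = .130. For f² = .0225 it is .0225 / 1.0225 = .022.

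**The case against.** The strongest reply is that nothing in the design changes. The ANOVA figure errs upward (236 against 164). The regression number is right once the symbol is corrected. The scale-validation requirement of 250 to 350 is larger than either, and 400 exceeds all of them. That stands, and it limits this to a correction of the text.

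The reply also has force against three stronger inferences that a reader might draw.

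- **That the survey is too small for its regressions.** The literal reading of f = .15 would need 523 to 998 respondents. But 160 matches f² = .15 exactly, and Appendix 2 calls the effect medium, so the evidence points to a mislabelled scale. The large figures show why the label must change; they do not show a shortfall.
- **That 160 belongs to an overall test and so contradicts the named R²-increase test.** The documents do not show this. Testing 10 of 13 predictors at f² = .15 also gives 160 (power .800). The hierarchical blocks in Appendix 2 item 5 allow that structure: 3 demographic terms first, then role (2 indicators), setting (3), seniority (1) and attitudes (4), which add to 10.
- **That power .95 was certainly the setting used.** It is the likeliest source, because it keeps every other stated input. But power .80 with a correlation of 0.9 also gives 236. Either the power or the correlation could be the misreported input.

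What the reply does not remove is that the stated ANOVA inputs do not return the stated ANOVA output, in either place.

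**Conclusion.** Wrong as written, in section 3.1.1 and in Appendix 2 item 7.

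- The ANOVA inputs need 164, so 236 is overstated by 72 respondents for the claimed power. With the other inputs held, 236 gives power .954.
- The regression's 160 is correct for f² = .15 and wrong for f = .15. The gap is between an R² of about 13% and one of about 2%.

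The ANOVA result assumes equal groups and a correlation of 0.5, the least favourable value the plan allows. The conclusion that 400 remains adequate assumes that f² = .15 was intended. If a true f of .15 had been meant, 400 would be too few however many predictors are tested, but the exact match at 160 argues against that.

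**What to change.** Retrieve the saved G*Power inputs for both calculations. Then, in section 3.1.1 and Appendix 2 item 7:

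1. Restate the ANOVA figure as either N = 164 at power .80 or N = 236 at power .95, whichever was run. If the saved file shows a different correlation, report that value instead.
2. Replace f = .15 with f² = .15.

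The cost is a few words in two places. The target of 400, the analyses and recruitment do not change.
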